**Table 2 Visit Window and Target day**

| Visit   | Target Study Day | Analysis Visit | Visit Window                           |
|---------|------------------|----------------|--|
| Visit 1 |                  | Screening      | < Time of First Dose                   |
| Visit 2 | 1                | Day 1          | Time of First Dose < Study Day ≤ Day 3 |
| Visit 3 | 8                | Day 8          | Day 4 < Study Day ≤ Day 11             |
| Visit 4 | 15               | Day 15         | Day 12 < Study Day ≤ Day 21            |
| Visit 5 | 28/ET            | Day 28/ET      | Day 22 < Study Day ≤ Day 34            |
| Visit 6 | 42               | Day 42         | Day 35 < Study Day ≤ Day 45            |

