9 STATISTICS

9.1 General Procedures

All personnel involved with the analysis of the study will remain blinded until database lock and identification of protocol deviations. Analyses will be performed using SAS® (SAS Institute, Cary, NC, US) by the sponsor or its representatives.

Details of all statistical summaries will be provided in the study-specific SAP. The SAP will be approved prior to any lock of the study database and unblinding of the study data. The SAP will provide a detailed description of the statistical methods and expand on the details provided in the protocol.

Patients will be stratified at randomization according to their baseline disease severity (moderate versus severe).

All data will be presented by treatment group. Descriptive statistics (number of observations, mean, standard deviation [SD], median, minimum, and maximum) will be provided for continuous variables, and counts and percentages will be presented for categorical variables.

Baseline is defined as the last non-missing measurement before or on the date of first administration of study medication.

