AD = atopic dermatitis; AE = adverse event; BSA = body surface area; EASI = Eczema Area and Severity Index; ECG = electrocardiogram; ET = Early Termination; HIV = human immunodeficiency virus; ICF = informed consent form; IGA = Investigator's Global Assessment; PK = pharmacokinetic; PP-NRS = Peak Pruritus Numerical Rating Scale; PTFU = Post-treatment Follow-up; SAE = serious adverse event; SARS-CoV-2 = severe acute respiratory syndrome coronavirus 2; WOCBP = women of child bearing potential

1. A written, signed ICF must be obtained from each patient prior to performing any study-related procedure.
2. A full examination will be performed at the Screening Visit. A full examination will include general appearance, skin, head, eyes, ears, nose, throat, neck, thyroid, chest/lungs, heart, abdomen, lymph nodes, and extremities. A brief examination will be performed at the Day 1 and Day28/ET Visits and any unscheduled visits and will include symptom-focused assessments.
3. Triplicate 12-lead ECGs will be obtained as outlined in [Section Error! Reference source not found..](#)
4. Vital signs will be measured in a semi-supine position after 5 minutes of rest and will include temperature, systolic and diastolic blood pressure, pulse, and respiratory rate. Height will be measured and recorded at the Screening Visit, and weight will be measured and recorded at each study visit.
5. Serum pregnancy test at the Screening Visit, urine pregnancy test at all other specified time points; for WOCBP only.
6. On dosing day(s), sampling for the analysis of clinical laboratory parameters will be performed before the administration of study medication.
7. PK samples will be drawn as outlined in [Section Error! Reference source not found..](#)
8. IGA and BSA assessed at the Screening Visit to ensure inclusion criteria are met. EASI, IGA, BSA, and PP-NRS assessed prior to study medication application on Day 1 to establish baseline and at study visits and end of the study (or ET) to document severity and extent of AD following study medication. The patient will complete the PP-NRS in their diary each morning before applying study medication during the Treatment Period.
9. Study medication will be applied at the site on study visit days, except Day 28 for PK subgroups 2 and 3. On Day 28, study medication will be applied at home to accommodate the timing of PK sample collection for PK subgroups 2 and 3.

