### 10.1.1. Study day and Visit Window

For each patient there will be a baseline period, a four-week treatment period and a two-week post treatment follow up period.

Study day is defined relative to the date of the first dose of study drug. For assessments that occur after this visit date, study day is calculated as (assessment date – first dose date + 1). For assessments that occur prior to first dose date, study day will be calculated as (assessment date – first dose date). There is no study Day 0. When there are multiple observations within a visit window, the value closest to the target day will be analyzed.

The visit window ([Table 2](#)) and PK draw window ([Table 3](#)) appear in the table below.

Table 2 will be used to define the analysis window for safety assessments (vital signs, ECGs, lab assessment) and for efficacy assessment of EASI, IGA, BAS, PP-NRS). Plasma concentrations will be summarized according to nominal time (no analysis visit windows) and may be plotted according to actual time relative to the time of first dose, as appropriate.

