### 10.1.2. Baseline

Baseline is defined as the last, non-missing measurement, before or on the date of first administration of study medication.

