### 12.6.5. Electrocardiograms

TriPLICATE 12-lead electrocardiograms (ECGs) will be obtained after the patient has been resting for at least 5 minutes at Screening and Day 28/ET.

Heart rate, PR interval, QRS axis, QRS duration, QT interval, RR interval, as well as the interpretation of the ECG will be collected in eCRF. All ECG results along with the interpretation by the central reader, including the average of triplicate measurements at each timepoint, will be presented in data listings.

QTcF values will be presented with the implementation of corrections (i.e., Fridericia's) as defined in ICH Guidelines E14 by the following categories:

Absolute QTcF interval prolongation:

- QTcF interval > 450 ms

- QTcF interval > 480 ms
- QTcF interval > 500 ms

Change from baseline in QTcF interval:

- QTcF interval increases from baseline >30 ms
- QTcF interval increases from baseline >60 ms.

The actual values and change from baseline values at each time point will be summarized for the FAS. An average of the triplicates at each timepoint will be used in the summaries. Baseline will be defined as the average of the last triplicate measurements before the first dose of study drug.

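### SAP Table 2 keeps the scheduled pre-dose Day 1 values out of the Day 1 visit, and the date-based baseline rule lets a same-day post-dose value become baseline

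*SAP*

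**What the plan says.** **Windows.** SAP Table 2 defines Screening as "< Time of First Dose", with no target day, and Day 1 as "Time of First Dose < Study Day ≤ Day 3". Section 10.1.1 makes the table binding for both safety and efficacy data: "Table 2 will be used to define the analysis window for safety assessments (vital signs, ECGs, lab assessment) and for efficacy assessment of EASI", with IGA, BSA and PP-NRS named next. Where a window holds several values, the same section selects the one nearest the target day.

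**Timing of Day 1 assessments.** Footnote 8 to SAP Table 1 has "EASI, IGA, BSA, and PP-NRS assessed prior to study medication application on Day 1 to establish baseline". Footnote 6 says that on dosing days "sampling for the analysis of clinical laboratory parameters will be performed before the administration of study medication". Footnote 4 on vital signs, and SAP 12.6.3, give position, rest and visits but nothing about before or after dosing.

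**Baseline.** SAP 10.1.2: "Baseline is defined as the last, non-missing measurement, before or on the date of first administration of study medication". Protocol 9.1 has the same rule: "Baseline is defined as the last non-missing measurement before or on the date of first administration of study medication". Two measures have a stricter rule of their own. For ECG, SAP 12.6.5 says: "Baseline will be defined as the average of the last triplicate measurements before the first dose of study drug". For PP-NRS, SAP 12.4.4.4 names the Day 1 score taken ahead of the application.

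**The concern.** There are two separate faults.

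First, the Day 1 window is on the wrong side of the dose. The scheduled Day 1 visit is a pre-dose visit for the efficacy scales and laboratory samples, but the window bearing its name accepts only values obtained after dosing. The real Day 1 values join the Screening values in a window with no target day, so the selection rule in 10.1.1 cannot choose between them.

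Second, the general baseline rule has no pre-dose condition. It uses the calendar date and takes the latest value on it. There is opportunity for a later value: the first application is made in clinic, the site is checked before discharge (Protocol 4.1.2), a PK sample follows at about 2 hours (Protocol 6.4), and an adverse event may prompt further vital signs, laboratory tests or EASI, IGA and BSA scoring (Protocol 4.2).

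At stake are by-visit tables that can be read as pre-treatment when they are not, and changes from baseline that start from a value already affected by the drug. In a first-in-human study, a change soon after the first application is one that the safety tables should be able to show.

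**Working it through.** No sample size, power or alpha figure in the plan depends on this point, so there is no stated figure to reproduce. The check applies the written rules to assessments around the first dose.

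**Step 1: windows and baseline eligibility.** Assume a first dose at 10:00 on Day 1. Table 2 compares a clock time with an integer study day, so both possible readings are shown. The date-only column takes the dosing date as Study Day 1, because the formulas in 10.1.1 cover only assessments before or after that date.

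| Assessment | Table 2, by date and time | Table 2, by date only | General baseline rule |
|---|---|---|---|
| Day 1, 09:00 (pre-dose) | Screening | no window | eligible |
| Day 1, 10:00 (exactly at dose) | no window | no window | eligible |
| Day 1, 12:00 (post-dose) | Day 1 | no window | eligible, and chosen over 09:00 because it is later |
| Day 2 | Day 1 | Day 1 | not eligible |
| Day 3 | Day 1 | Day 1 | not eligible |

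Under neither reading does the scheduled pre-dose value fall in Day 1.

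**Step 2: what shares the Screening window.** By date and time, EASI, IGA, BSA and laboratory tests have two scheduled values there, one from the Screening Visit and one from Day 1. PP-NRS is not scheduled at Screening, so its Day 1 value is alone there and is simply mislabelled. Vital signs split: those taken before dosing go to Screening, those taken after go to Day 1.

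**Step 3: which baselines are exposed.**

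| Measure | Rule or timing stated | Can a post-dose value become baseline? |
|---|---|---|
| PP-NRS | own pre-dose baseline, SAP 12.4.4.4 | no |
| ECG | own pre-dose baseline, SAP 12.6.5; not scheduled on Day 1 | no |
| EASI, IGA, BSA | scheduled pre-dose, footnote 8; general baseline rule | only if repeated or done late on Day 1 |
| Laboratory tests | scheduled pre-dose, footnote 6; general baseline rule | only if repeated or done late on Day 1 |
| Vital signs | no timing relative to dose; general baseline rule | yes, even when done as scheduled |

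**Step 4: effect on one patient (invented values).** Pulse is 70 before dosing, 95 when repeated after dosing on Day 1, and 80 on Day 8.

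- Baseline under the written rule is 95, so change = 80 - 95 = -15.
- Baseline under a pre-dose rule is 70, so change = 80 - 70 = +10.

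The two differ by 95 - 70 = 25, and the direction is reversed.

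**The case against.** The strongest reply is that the intention is plain and little follows from the slip. Much of this stands, and it rules out several stronger conclusions that a reader might draw.

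- **That the window error changes baseline or the primary result.** It does not by itself. SAP 10.1.2 and 10.1.3 derive baseline and change without using Table 2, so a pre-dose Day 1 EASI labelled Screening is still the baseline. The primary summary in 12.4.3.4 reports baseline and Week 4, not a Day 1 row.
- **That a reaction visit on Days 1 to 3 would appear as Day 1 in the safety tables.** For laboratory tests and vital signs, SAP 12.6.2 and 12.6.3 limit by-visit summaries to scheduled assessments, so unscheduled values stay out. Read literally, the laboratory Day 1 row is then empty, and the vital-signs row holds only scheduled values that happened to be taken after dosing.
- **That ECG alone has a pre-dose baseline.** PP-NRS has one too, and footnote 8 shows that the same was meant for EASI, IGA and BSA.
- **That an immediate reaction would go unseen.** It would still be reported as a treatment-emergent event, and as an event of special interest if at the application site. All laboratory and vital-sign values are listed. What can be distorted is the change from baseline.

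The appeal to intention does not stand in full. Section 10.1.1 prescribes the Table 2 windows, footnote 8 does not cover vital signs, and no footnote settles which value counts when a measurement is repeated the same day. The limit to scheduled assessments is written for by-visit summaries and does not appear in the baseline definition. The explicit pre-dose wording for ECG and PP-NRS makes its absence from the general rule more noticeable.

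**Conclusion.** The point holds as two wording errors in the SAP that should be corrected before database lock. Neither is shown to threaten the primary analysis.

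The window error affects every FAS patient for each measure scheduled before dosing on Day 1, but its effect is on labels: the Day 1 row loses its intended values, and Screening holds two sets with no rule to choose between them.

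The baseline error reaches fewer values but matters more where it occurs. Vital signs are the main exposure. Laboratory tests, EASI, IGA and BSA are exposed only through a repeat or a late assessment on Day 1, and the primary endpoint only through such an EASI. The documents give no basis for estimating how often this would happen, and the pulse figures show direction only.

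The conclusion assumes that Table 2 and 10.1.2 would be programmed as written. If nominal visits and clock times were used instead, the tables would be right, but not because of the plan.

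**What to change.** Amend the SAP before database lock.

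1. **Table 2.** Screening: study days before Day 1. Day 1 (Baseline): Study Day 1, at or before the time of first application. Do not move post-dose Day 1 to Day 3 values into the Day 8 window; list them as unscheduled. Otherwise, in a patient who misses the Day 8 visit, a Day 2 score could be selected as the Day 8 value and enter the repeated-measures model.
2. **Section 10.1.2.** Baseline: the last non-missing value before the first application, judged by date and time. A scheduled Day 1 assessment with no recorded time, or with the same recorded time as the application, counts as pre-dose. This brings the general rule into line with those for PP-NRS and ECG.
3. **Section 6.1.** Record that the SAP tightens the date-based definition in Protocol 9.1. No change to the protocol or to site instructions is needed.

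The cost is minor programming and no new data. The downside is an assumption about timing where no clock time was recorded. It is weakest for vital signs, so the number of baselines resting on it could be footnoted.

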#### 12.4.4. Secondary Analyses

Treatment comparisons between ATI-1777 and vehicle for each of the continuous efficacy endpoints that are conducted over time (change in IGA, BSA, and PP-NRS) will be analyzed using a similar model as described for the primary endpoint. Treatment comparisons will be made for each post-baseline scheduled visit utilizing the analysis window scheme described in [Section 10.1.1](#). Change from baseline is calculated as described in [section 10.1.3](#).

Treatment group comparisons for categorical efficacy endpoints (IGA response, EASI-50, EASI-75, and EASI-90) that are conducted over time will employ a logistic regression model fit at each scheduled visit separately, where appropriate. The logistic regression model will include treatment group and baseline severity of AD as a factor, and the baseline value as a covariate. Model-based point estimates for the treatment proportions will be provided as well as model-based differences and corresponding symmetric 90% confidence intervals and one-sided p-values. If the Logistic model will not converge or if there is strong collinearity between the baseline EASI score and the baseline severity of AD, one or both of the covariates may be excluded from the secondary analysis.

The secondary efficacy endpoints are

- Percent change from baseline in EASI score at each study visit
- Proportion of patients achieving an IGA score of 0 to 1 combined with an improvement of 2 or more points from baseline within 4 weeks of the start of treatment
- Proportions of patients who achieve EASI-50, EASI-75, and EASI-90 within 4 weeks of the start of treatment
- Change from baseline in IGA score at each study visit
- Change from baseline in BSA at each study visit
- Change from baseline in PP-NRS score over time

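### SAP Table 2 leaves study Days 4, 12, 22 and 35 in no analysis window, so a protocol-compliant Day 12 assessment is not assigned to the Day 15 visit

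*SAP*

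**What the plan says.** SAP Table 2 sets the post-Day 1 analysis windows as follows: Day 8, "Day 4 < Study Day ≤ Day 11"; Day 15, "Day 12 < Study Day ≤ Day 21"; Day 28/ET, "Day 22 < Study Day ≤ Day 34"; Day 42, "Day 35 < Study Day ≤ Day 45". The Day 1 row runs from the time of first dose to Day 3 inclusive.

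SAP Section 10.1.1 defines the unit: for assessments after the first dose, "study day is calculated as (assessment date – first dose date + 1"). It also sets the scope: "Table 2 will be used to define the analysis window for safety assessments", and the same sentence extends the windows to EASI, IGA, BSA and PP-NRS. SAP Section 12.4.4 ties the secondary analyses to them: "Treatment comparisons will be made for each post-baseline scheduled visit utilizing the analysis window scheme described in" Section 10.1.1. For the responder endpoints, Section 12.4.4 says the plan "will employ a logistic regression model fit at each scheduled visit separately, where appropriate".

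The Schedule of Events (Table 1 in both documents) allows the Day 15 visit ±3 days. Under SAP Section 12.4.2, missing continuous data are filled by LOCF in the full analysis set (FAS) and left missing in the per-protocol (PP) set; a missing responder result counts as non-response.

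**The concern.** Each window closes on an inclusive day, and the next opens strictly after the following day. On a whole-number day scale this drops one day at every boundary. One of the dropped days, Day 12, is a permitted day for the Day 15 visit, so a patient who keeps to the schedule can have EASI, IGA and BSA records that the SAP assigns to no visit.

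By-visit EASI, IGA and BSA are listed secondary endpoints. A programmer must either follow the table and set aside observed, on-schedule data, or depart from the SAP without a documented rule. A choice of that kind should be settled before unblinding.

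**Working it through.** The plan states no figure to reproduce here. The check applies the printed limits to each whole study day and then sizes the consequences under stated assumptions.

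**1. Coverage.** Inputs: the Table 2 limits and the Table 1 tolerances. The Day 1 row is read as including Day 1 after dosing, because its lower limit is a dose time.

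| Analysis visit | Days covered as printed | Permitted visit days | Permitted but unassigned |
|---|---|---|---|
| Day 1 | 1–3 | – | – |
| Day 8 | 5–11 | 5–11 (8 ± 3) | none |
| Day 15 | 13–21 | 12–18 (15 ± 3) | Day 12 |
| Day 28/ET | 23–34 | 26–30 (28 ± 2) | none |
| Day 42 | 36–45 | 39–45 (42 ± 3) | none |

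The unassigned days from 1 to 45 are exactly 4, 12, 22 and 35. Days 4, 22 and 35 can arise only from early-termination, unscheduled or out-of-window visits.

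**2. Could another rule rescue Day 12?**
- The closest-to-target rule in SAP 10.1.1 chooses among observations already inside a window.
- The ET rule in SAP Section 10 applies only to patients who leave the study early.
- PP-NRS has its own selection rule (SAP 12.4.4.4), so it is outside the problem.
- The laboratory text (SAP 12.6.2) can be read as keeping a scheduled draw under the visit it was recorded for. The vital-signs text (SAP 12.6.3) has no such qualifier.
- Nothing assigns a Day 12 EASI, IGA or BSA record to Day 15.

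**3. Number affected (assumption).** The documents give no count. Take k = 2 to 7 of the protocol's 50 patients (4% to 14%). The upper value is an even spread over the 7 permitted days: 50/7 ≈ 7.

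**4. FAS, Day 15 EASI difference.** If the Day 12 record counts as the last observation, it is carried to Day 15 and the shift is 0. If only windowed records count, Day 8 is carried forward and

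expected shrinkage = (k/50) × (difference at Day 15 − difference at Day 8).

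- Assumed differences of 35 and 20 points (gain 15): 2/50 × 15 = 0.6; 7/50 × 15 = 2.1.
- Gain 5: 0.2 to 0.7. Gain 25: 1.0 to 3.5.

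For scale, take the sample-size section's 38.3 as an SD, with 25 patients per arm. The unadjusted standard error of a difference is 38.3 × √(2/25) ≈ 10.8 points. So 0.6 to 2.1 points is about 0.06 to 0.19 standard errors, and 3.5 points about 0.32.

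**5. PP, Day 15 standard error.** With k Day 15 values lost at random, evenly across arms, and the other visits complete:

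SE ratio = √[(1 − R²) × n/(n − k) + R²],

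where R² is the squared multiple correlation of Day 15 with Days 8 and 28. Assumed correlations (Days 8–15, 15–28, 8–28):
- 0.3/0.3/0.2: R² = (0.09 + 0.09 − 2 × 0.09 × 0.2)/(1 − 0.04) = 0.15.
- 0.8/0.8/0.65: R² = (0.64 + 0.64 − 2 × 0.64 × 0.65)/(1 − 0.4225) ≈ 0.776.

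| n | k | Ratio, R² = 0.776 | Ratio, R² = 0.15 | No borrowing, √(n/(n − k)) |
|---|---|---|---|---|
| 50 | 2 | 1.005 | 1.018 | – |
| 50 | 7 | 1.018 | 1.067 | √(50/43) = 1.078 |
| 34 | 1 | 1.003 | 1.013 | – |
| 34 | 5 | 1.019 | 1.071 | √(34/29) = 1.083 |

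Random loss brings no expected bias. The Week 4 ratio is 1.000 in every case, because Day 28 data stay complete.

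**6. Day 15 responder difference, if fitted.** With both arms equally affected, it is multiplied by 1 − k/50:
- Assumed 50% vs 20%: 30 points becomes 30 × 0.96 = 28.8, down to 30 × 0.86 = 25.8.
- Assumed 30% vs 15%: 15 points becomes 14.4, down to 12.9.

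**7. After correction.** With inclusive lower limits the windows are Days 4–11, 12–21, 22–34 and 35–45. Each of Days 1 to 45 then falls in exactly one window, and every Table 1 tolerance maps to its own visit.

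**The case against.** The strongest reply is that this is a typographical slip. The paired limits (3/4, 11/12, 21/22, 34/35) make sense only if the lower limits were meant to be inclusive, and a sensible programmer would read them so. That intent is very likely, but the rule as written says otherwise, and the analyses are bound to the rule.

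A second point is that the literal reading is selective: applied to the Day 1 row, it might exclude Day 1 as well. That row is bounded by the time of the first dose, so post-dose Day 1 fits it naturally, and the other four gaps do not depend on it.

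Third, the consequences are conditional and small. This stands. The ordinary reading of LOCF carries the Day 12 value itself, giving no FAS shift. The EASI responder definition and example code in SAP 12.4.4.1 use Day 28, so a Day 15 fit may never be run. PP loses only precision. The sizes rest on assumed inputs and are small against a standard error of about 10.8 points at an unadjusted secondary time point.

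Fourth, the correction does not cover every permitted follow-up day. Protocol 4.1.3 times follow-up from the Day 28/ET visit, so a Day 30 visit allows follow-up to 30 + 14 + 3 = Day 47, past the Day 45 limit. That is true but separate: no EASI, IGA or BSA is scheduled then.

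**Conclusion.** The concern holds. As printed, Table 2 assigns Days 4, 12, 22 and 35 to no window, and a compliant Day 12 visit is lost to the Day 15 analysis visit. That part rests on the documents alone.

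The effect is confined to Day 15 secondary efficacy results and some by-visit safety summaries. Its size rests on the assumed 2 to 7 of 50 Day 12 visits and on the assumed differences, correlations and response rates shown above. On those assumptions it ranges from nothing to modest.

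On-schedule Week 4 values and Day 28 responder status are unaffected, and the effect on the primary result is negligible. One small route remains: if a patient's last record is on Day 12, whether it is carried to Week 4 turns on the same LOCF ambiguity. The point should be fixed because the rule is wrong as written and the repair is trivial, not because it threatens the main conclusion.

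**What to change.** Before database lock, change the four strict lower limits in SAP Table 2 to inclusive ones: Day 4 ≤, Day 12 ≤, Day 22 ≤ and Day 35 ≤ Study Day. The cost is four inequality signs in one SAP table, with no protocol or operational change.

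Two optional clarifications could go in at the same time, though the fix does not need them: cross-refer Table 2 to the ET rule in SAP Section 10, and reconcile the Day 45 upper limit with the follow-up timing in Protocol 4.1.3.

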### 12.4.2. Imputation Methods

For the continuous efficacy analysis on the FAS population, missing data will be imputed using last observation carried forward (LOCF). Missing data will not be imputed for continuous efficacy analyses that are based on the PP population. For responder-type categorical endpoints (such as EASI-50, EASI-75, and EASI-90), missing data will be treated as a non-response.

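### SAP Table 2 puts Days 4, 12, 22 and 35 in no analysis window, and Day 12 is a permitted day for the Day 15 visit

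*SAP*

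**What the plan says.** SAP Section 10.1.1 computes study day from dates as a whole number and assigns assessments to visits through Table 2. The windows for Visits 3 to 6 are:

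- Day 8: "Day 4 < Study Day ≤ Day 11"
- Day 15: "Day 12 < Study Day ≤ Day 21"
- Day 28/ET: "Day 22 < Study Day ≤ Day 34"
- Day 42: "Day 35 < Study Day ≤ Day 45"

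The preceding Day 1 window ends at Day 3. Table 2 applies to vital signs, ECGs and laboratory data "and for efficacy assessment of EASI, IGA, BAS, PP-NRS" (BAS is evidently BSA). Only plasma concentrations are exempt; they are summarized by nominal time. The one tie-break rule in the section chooses between observations that are already inside a window.

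SAP Section 12.4.4 relies on the scheme: "Treatment comparisons will be made for each post-baseline scheduled visit utilizing the analysis window scheme". Under SAP Section 12.4.2, missing continuous efficacy data are filled by LOCF on the FAS and are not imputed on the per-protocol set. For responders: "For responder-type categorical endpoints (such as EASI-50, EASI-75, and EASI-90), missing data will be treated as a non-response".

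The Schedules of Events (Table 1 in both documents) allow Day 8 ±3, Day 15 ±3, Day 28 ±2 and Day 42 ±3 days. Protocol Sections 4.1.2 and 4.1.3 time the follow-up visit differently, at 2 weeks ±3 days after the actual Day 28/ET visit.

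**The concern.** Each window closes on an inclusive upper bound, and the next opens with a strict inequality on the following day. That following day belongs to neither window. For Day 12, this means a visit that complies fully with the protocol yields efficacy data with no analysis visit, and neither document gives a fallback for such efficacy data.

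Three things follow from the SAP's own rules for a patient seen on Day 12:

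- On the FAS, the Day 15 value of a continuous endpoint is imputed although it was observed. If LOCF works on windowed data, the Day 8 value is carried. The SAP does not say whether an unwindowed Day 12 value may itself be carried, so two programmers could produce different data sets.
- On the per-protocol set, the Day 15 value is missing.
- In any Day 15 responder analysis, the patient is a non-responder whatever the score.

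SAP Section 12.4.4.1 makes the EASI estimates at visits other than Week 4 secondary endpoints, so these are reported results. PP-NRS is left out here because it is recorded daily and the score for each visit day is flagged (SAP Section 12.4.4.4).

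**Working it through.** **Coverage.** The inputs are the bounds in SAP Table 2, the tolerances in Table 1 and the follow-up rule in protocol Section 4.1.3. The printed inequalities are applied to each whole study day.

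| Visit | Days held as printed | Permitted days | Permitted but not held |
|---|---|---|---|
| 3 (Day 8) | 5–11 | 5–11 | none |
| 4 (Day 15) | 13–21 | 12–18 | 12 |
| 5 (Day 28/ET) | 23–34 | 26–30 | none |
| 6 (Day 42) | 36–45 | 39–45 by Table 1; 37–47 by Section 4.1.3 | 46, 47 |

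- Days in no window from Day 4 to Day 45: 4, 12, 22 and 35, which is 4 of 42.
- Permitted days for the three post-baseline efficacy visits: 7 + 7 + 5 = 19. One is lost, Day 12.
- Follow-up range: 26 + 14 − 3 = Day 37 to 30 + 14 + 3 = Day 47. Days 46 and 47 lie beyond the last window. EASI, IGA, BSA and PP-NRS are not scheduled at that visit.
- With `≤` at the four lower bounds, the windows are Days 4–11, 12–21, 22–34 and 35–45, with no gap and no overlap.

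**Share of patients.** The documents give no distribution of visit days. I assume that between 0 and 1/7 of Day 15 visits fall on Day 12. The upper end means visits spread evenly over the seven permitted days. With 50 patients this is 0 to 50/7 ≈ 7.

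**Responder analyses at Day 15.** With 25 patients per arm, each Day 12 responder counted as a non-responder lowers that arm's rate by 1/25 = 4 percentage points. If Day 12 attendance is equally common in both arms, and the response difference among these patients equals that in the others, the rate difference shrinks by 0 to 1/7, or 0 to 14%.

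**Continuous EASI at Day 15, FAS.** The question is how much larger the treatment difference is on Day 12 than on Day 8, because the Day 8 value would replace the Day 12 value. The Week 4 difference is the planned 65 − 20 = 45 points. The time course is my assumption. With t as days since Day 1:

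- Linear: D(t) = 45 × t/27, so D(11) − D(7) = 45 × 4/27 = 6.7.
- Exponential: D(t) = 45 × (1 − e^(−t/τ)) / (1 − e^(−27/τ)). D(11) − D(7) is 3.2 for τ = 3 days, 7.4 for τ = 7, 8.0 for τ = 12 and 7.8 for τ = 20.

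The range is 3.2 to 8.0 points. At the upper share of 1/7, the understatement is 3.2/7 ≈ 0.5 to 8.0/7 ≈ 1.1 points; at a share of 0 it is 0.

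**Scale.** The plan calls 38.3% a variance. I read it as a standard deviation: with 17 per arm, a difference of 45 and one-sided α = 0.05, that reading gives 95.6% power by the noncentral t, which is the plan's stated figure. The standard error with 25 per arm is 38.3 × √(2/25) ≈ 10.8, so 1.1 points is about a tenth of a standard error.

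**The case against.** The strongest reply is that this is a drafting slip. The bounds 3/4, 11/12, 21/22 and 34/35 are plainly meant to be contiguous, and many programmers would code them so. This is probably right about intent. It does not change what the rule says, and a SAP should not depend on a programmer departing from it.

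The reply is also right that little is at stake. The analysis affected is one intermediate visit, with secondary status and no multiplicity control, in a preliminary-efficacy trial. The responder endpoints are worded as response within 4 weeks, SAP Section 12.4.4.1 defines EASI-50 by example at Day 28, and Section 12.4.4 fits by-visit logistic models only where appropriate. The responder effect therefore arises only if a Day 15 model is actually fitted. A 1/7 share is also likely to be generous for the edge of a window centred on Day 15.

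Three stronger readings are tempting, and the documents do not support them:

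- *All four gap days lose on-time data.* Only Day 12 is inside a scheduled tolerance. Days 4, 22 and 35 matter only for scheduled visits outside tolerance, unscheduled visits, or visits related to early termination.
- *The primary endpoint loses data.* Days 26 to 30 all lie inside the Day 28/ET window. For patients who leave early, SAP Section 10 uses the data from each visit attended, and goes back to the previous visit if the ET visit came more than 1 day after the last dose. That wording refers to visits, not windows, so a Day 12 visit can still serve. The opposite claim, that Week 4 cannot move at all, also goes too far: all visits share one MMRM (SAP Sections 12.4.3.4 and 12.4.4.1), so altered or absent Day 15 values could shift the Week 4 contrast slightly.
- *Day 12 laboratory results drop out of the summaries.* SAP Section 12.6.2 reports laboratory data by the visit window for which they were recorded. This can be read as assignment by nominal visit, so the loss is not established. No such wording exists for efficacy data.

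**Conclusion.** The rule is wrong as written. Days 4, 12, 22 and 35 have no analysis window, and Day 12 is a permitted day for the Day 15 visit, so an on-time EASI, IGA or BSA assessment can have no Day 15 value. That much follows from the two tables alone and needs no assumption.

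The size is small and falls mainly on the Day 15 secondary analyses. The numerical ranges rest on the assumed 0 to 1/7 share of Day 12 visits, 25 patients per arm, the planned 45-point difference, the assumed time courses, and LOCF carrying the Day 8 value. The possible shift in the Week 4 contrast through the joint model is not quantified; the patient's own Week 4 value normally stands. The unwindowed follow-up Days 46 and 47 concern safety data only.

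**What to change.** In SAP Table 2, change the lower bounds for Visits 3 to 6 from `<` to `≤`, and extend the Visit 6 upper bound from Day 45 to Day 47. The windows become Days 4–11, 12–21, 22–34 and 35–47, and every day from 4 to 47 belongs to exactly one.

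Make the change before unblinding, so that the placement of Day 12 data is not decided with results in view. SAP Section 6 already places final approval before database lock and unblinding. It also foresees updates when the protocol changes, and one is due: the SAP cites protocol V2.0 and plans 42 patients, while the current protocol is Version 4 with 50.

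The cost is four symbols and one number. No visit, sample or analysis is added.
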